1) Identify the rate at which blindly placed caudal blocks are not within the epidural space 2) Identify the rate at which ultrasound can guide a wrong block into the correct location 3) Identify if lack of heart rate change on incision can predict successful placement when medication administration is successfully confirmed with ultrasound 4) Identify if after using ultrasound to visualize placement, if concentrations of inhaled agents may be reduced in children

Section E: Protocol Risks/Subjects

E1. Risk Category

Category 1: Research not involving greater than minimum risk.

E2. Subjects

Gender:

Both

Age:

Child (3-12 yrs), Infant/Toddler (0-36 mos)

Ethnicity:

All Ethnicities

Primary Language:

English, Spanish

Groups to be recruited will include:

Patients

Which if any of the following vulnerable populations will be recruited as subjects?

Children

Vulnerable populations require special protections. How will you obtain informed consent, protect subject confidentiality, and prevent undue coercion?

Consent will only be obtained from parents/legal guardians. Confidentiality will be maintained by the PI as no patient or provider specific identifiers will be recorded aside from consent parental signature. To avoid undue coercion, consenting parents/guardians will be informed that their willingness to participate will not affect their child's treatment course or ability to get a caudal block or have any impact on their care course.

E3. Pregnant woman/fetus

Will pregnant women and/or fetuses (as described in 45 CFR 46 Subpart B) be enrolled in the research?

No

E4. Neonates

Will neonates of uncertain viability or nonviable neonates (as described in 45 CFR 46 Subpart B) be enrolled in the research?

No

E5. Children

Will children be enrolled in the research?

Yes

Section F: Design/Procedure

F1. Design

Select one category that most adequately describes your research:

c) Pilot

Discuss the research design including but not limited to such issues as: probability of group assignment, potential for subject to be randomized to placebo group, use of control subjects, etc.

Single blinded prospective trial in which all patients serve as their own clinical control group.

Inclusion Criteria:

Children ages 0-84 months Infra-umbilical procedure for which a caudal block is already planned American Society of Anesthesiology classifications of 1,2 or 3

Exclusion Criteria:

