Associated procedures for which caudal does not provide complete analgesia Incarcerated hernias Emergency procedures Local Anesthetic allergy Sacral dimple Rash over sacrum precluding block Parents/legal guardians unable to consent for surgical procedure in English language Foster Care/Child protective services as guardians Parental Refusal for caudal block or study participation American Society of Anesthesiology classifications other than 1,2 or 3

F2. Procedure

Patients meeting inclusion criteria and following informed consent will be brought back to the operating room. General anesthesia will be induced in the standard manner either by inhalation induction or intravenous induction at the discretion of the anesthesia attending of record. The airway will be secured using an

age/weight appropriately sized device, at the discretion of the anesthesia attending of record. The caudal block will ensue in the same manner regardless of the study at the discretion of the anesthesia attending of record. The attending anesthesiologist will perform or instruct the placement of a caudal block according to their standard of practice. At the time of administration of local anesthetic into the caudal space, the study collaborator (SC) will ultrasound the caudal space keeping the provider placing the block blinded to the imaging. The provider placing the block will inject 0.5mL of preservative free saline. The provider will then be asked to state if they are correctly in the caudal space or not. If the provider feels they are not in the caudal space, they will re-do the procedure. If the provider fails to identify incorrect location and this is noted by ultrasound, the SC will inform the provider to re-do the procedure. After a successful injection (as confirmed by ultrasound) is performed, the patient will be prepped for the procedure in standard manner. The inhaled anesthetic will be titrated until the minimal alveolar concentration is between 0.8-1 MAC for age prior to incision. The anesthesia provider will note the heart rate immediately before and after the first surgical stimulation. Data will be recorded de-identified on the sheet (see attached). The study PI will compare MAC hours (exposure to inhaled anesthetic agent) in patients having undergone caudal block with ultrasound confirmation to those in the retrospective group gathered for quality improvement to ascertain if reduction of exposure to inhaled agent was possible.

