Patient: For the individual patient enrolled, there will be no deviation from the standard of practice of either the anesthetic or regional block. As nearly all providers perform this technique blindly, the patient will have the benefit of immediate recognition of incorrect block eliminating the possibility for inadvertent sham block. In addition, reduced block failure will result in less exposure to opioids and inhaled anesthetic agents.

Describe potential benefit(s) to society of the planned work.

The benefit from this study, should it show that ultrasound is superior for recognizing incorrect placement when compared with blind technique is that fewer inadvertent sham blocks may be performed. Additionally, if reduction of block failure by use of ultrasound can be established, reduced exposure to inhaled anesthetics which have potential adverse effects on neurodevelopment may be possible

Do anticipated benefits outweigh potential risks? Discuss the risk-to-benefit ratio.

The study benefits the participant that would undergo a caudal block using a blind technique in that immediate recognition of sham block would be possible allowing for correction of placement. The study would reduce the risk for patients undergoing caudal blocks with incorrect placement that provide a risk of the block with no benefit. This allows the patient to either benefit from the block or avoid wrongly placed medication should the block be aborted. As with all studies, there is a small risk of loss of confidentiality or data breach.

Section J: Consent Procedures

J1. Waiver of Consent

Will any portion of this research require a waiver of consent and authorization?

NA

J1a. Waiver of requirement for written documentation of Consent

Will this research require a waiver of the requirement for written documentation of informed consent?

NA

J2. Consent Procedures

Who will recruit subjects for this study?

PI
PI's staff

Describe how research population will be identified, recruitment procedures, any waiting period between informing the prospective participant and obtaining consent, steps taken to minimize the possibility of coercion or undue influence and consent procedures in detail.

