The PI or approved collaborators as listed in this protocol will recruit patients that will be undergoing procedures for which a caudal block will already be provided as standard of care. Consent for the anesthetic including the caudal block will be taken by the attending anesthesiologist of record or designated associate (resident/fellow). If inclusion/exclusion criteria are met, the PI or approved collaborators will approach the consenting parent for consent. The parent will be informed that no changes to their child's care will be made by participation in this study. They will be informed that study participation is not required and that failure to participate will not, in any way alter the care provided to their child. They will also be informed that consent for participation can be withdrawn at any time.

Are foreign language consent forms required for this protocol?

Yes

Which of the following ways will you document informed consent in languages other than English?

Short-Form consent documents

J3. Privacy and Intrusiveness

Will the research involve observation or intrusion in situations where the subjects would normally have an expectation of privacy?

No

J4. Children

Will children be enrolled in the research?

Yes

J5. Neonates

Will non-viable neonates or neonates of uncertain viability be involved in research?

No

J6. Consent Capacity - Adults who lack capacity

Will Adult subjects who lack the capacity to give informed consent be enrolled in the research?

No

J7. Prisoners

Will Prisoners be enrolled in the research?

No

Section K: Research Related Health Information and Confidentiality

Will research data include identifiable subject information?

NA

Information from health records such as diagnoses, progress notes, medications, lab or radiology findings, etc.

NA

Specific information concerning alcohol abuse:

NA

Specific information concerning drug abuse:

NA

Specific information concerning sickle cell anemia:

NA

Specific information concerning HIV:

NA

Specific information concerning psychiatry notes:

NA

Demographic information (name, D.O.B., age, gender, race, etc.):

NA

Full Social Security #:

NA

Partial Social Security # (Last four digits):

NA

Billing or financial records:

NA

Photographs, videotapes, and/or audiotapes of you:

NA

Other:

NA

At what institution will the physical research data be kept?

NA

How will such physical research data be secured?

NA

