At what institution will the electronic research data be kept?

NA

Such electronic research data will be secured via BCM IT Services- provided secured network storage of electronic research data (Non-Portable devices only):

NA

Such electronic research data will be secured via Other:

NA

Will there be anyone besides the PI, the study staff, the IRB and the sponsor, who will have access to identifiable research data?

NA

Please describe the methods of transmission of any research data (including PHI, sensitive, and non-sensitive data) to sponsors and/or collaborators.

NA

Will you obtain a Certificate of Confidentiality for this study?

No

Please further discuss any potential confidentiality issues related to this study.

The PI will de-identify all data using a random number generator to create a study number. Only the PI will have access to the patients medical record number which will not be shared between collaborators. this will be stored on a separate paper in a secured locked drawer in the secured anesthesia office at TCH

Section L: Cost/Payment

Delineate clinical procedures from research procedures. Will subject's insurance (or subject) be responsible for research related costs? If so state for which items subject's insurance (or subject) will be responsible (surgery, device, drugs, etc). If appropriate, discuss the availability of financial counseling.

Standard of care will be applied No additional charges are to be acquired by the patients from participation in the study

If subjects will be paid (money, gift certificates, coupons, etc.) to participate in this research project, please note the total dollar amount (or dollar value amount) and distribution plan (one payment, pro-rated payment, paid upon completion, etc) of the payment.

Dollar Amount:

0

Distribution Plan:

N/A

Section M: Genetics

How would you classify your genetic study?

Discuss the potential for psychological, social, and/or physical harm subsequent to participation in this research. Please discuss, considering the following areas: risks to privacy, confidentiality, insurability, employability, immigration status, paternity status, educational opportunities, or social stigma.

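### J2 and Section I say that taking part changes nothing in care, but F2 adds a collaborator ultrasound for every child and a possible collaborator-directed repeat block, and Section H names no physical risk

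*Combined protocol and SAP*

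**What the plan says.** **On care being unchanged.** Section I, on the individual patient, says "there will be no deviation from the standard of practice of either the anesthetic or regional block". J2 sets out what staff will say at consent: "The parent will be informed that no changes to their child's care will be made by participation in this study".

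**On what is done.** F2 begins with usual practice: "The caudal block will ensue in the same manner regardless of the study at the discretion of the anesthesia attending of record". It then adds study steps. At injection, "the study collaborator (SC) will ultrasound the caudal space keeping the provider placing the block blinded to the imaging". Next, "The provider placing the block will inject 0.5mL of preservative free saline", and the provider must say whether the needle is in the caudal space. A provider who thinks it is not repeats the block. If the provider does not recognize a misplacement and the ultrasound shows it, the collaborator tells the provider to repeat it. After confirmed placement, the inhaled agent is brought to 0.8-1 MAC for age before incision.

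**On risk and benefit.** Section H states no risk of discomfort and names only loss of confidentiality or a data breach. Section I counts prompt detection and correction of a misplaced block among the benefits to the participant.

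**On objective 4.** F2 compares MAC hours in study patients with those in the earlier quality-improvement audit group. The background text before Section D gives that audit's failure rate as 18%, with failure defined as a heart rate rise of more than 20% at incision despite a block and more than 1 MAC.

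**The concern.** J2 is an instruction to staff about what to tell parents of children aged 0-84 months. If staff follow it as written, they say something that F2 makes untrue. The added steps are probably in the child's interest, but a parent is entitled to know that a second person will scan the child and may have the needle placed again. Section H is where that repeat placement should appear, and it does not.

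The secondary matter is inferential. The plan fixes a depth window before incision in the study patients, then compares their anesthetic exposure with that of a group treated earlier under conditions it does not describe. Unless the plan says how a difference will be read, a lower MAC-hours figure could be reported as an effect of ultrasound confirmation when part of it may come from the window or from the comparator.

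**Working it through.** The plan states no figure on this point, so there is none to reproduce. The check sets the sections side by side.

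**1. Is the scan usual care?** The background text cites a registry review in which ultrasound was reported in under 3% of caudal blocks, and Section I says that nearly all providers work blind. F2 has a collaborator scan every enrolled child. The scan therefore comes from the study, for 150 of 150 children (G1). The same holds for the stated judgment, which F2 asks of every provider.

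**2. Is the repeat placement usual care?** F2 has two routes to a repeat.
- The provider recognizes the misplacement and repeats the block. This would happen without the study.
- The provider does not recognize it, the scan shows it, and the collaborator directs a repeat. Without the scan there would be no trigger at that moment. This repeat is attributable to the study.

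**3. Does the protocol treat it as a change?** Yes. Section I presents immediate detection and correction as something gained by a child who would otherwise have a blind block. That gain exists only if the block is managed differently. The no-deviation sentence and the benefit claim stand in the same section and cannot both be taken literally.

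**4. Does Section H cover it?** No. The risk-benefit paragraph in Section I also gives confidentiality as the only risk of the study, although it accepts that a misplaced block carries risk without benefit.

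**5. Steps whose status is unknown.** The 0.5 mL saline injection and the 0.8-1 MAC window are specified in F2. The documents do not say whether either is already local practice.

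**6. MAC hours.**
- Study patients: 0.8-1 MAC before incision, by protocol.
- Audit failures, 18%: above 1 MAC, by definition.
- Remaining audit patients, 100% - 18% = 82%: depth not given.
- The audit group is retrospective, so it is non-concurrent, and it is not shown to have used the study window.

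A difference in MAC hours therefore mixes the effect of confirmation, the effect of the prescribed window, and any differences between periods and patients. The documents give nothing from which to size these parts.

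**The case against.** The best defense is that the provider's technique really is unchanged and the study only adds a check. Section I describes that check and its consequence openly a sentence later, so nothing is concealed. The redo replaces a block that would probably have failed, it follows a small saline test, the background text calls caudal access extremely low risk, and the block has its own clinical consent. Most of this is right, and it is why the point is modest. It does not rescue J2, whose sentence is not limited to the initial placement.

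Several stronger readings are tempting, and the documents do not support them.

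- *That E2 makes the same false statement.* Its wording, "or ability to get a caudal block or have any impact on their care course", has willingness to participate as its subject and answers a prompt about coercion. It assures parents that refusing carries no penalty, and it should stay.
- *That Section L does so.* The prompt is "Delineate clinical procedures from research procedures" and the reply is "Standard of care will be applied", followed by a statement that there are no extra charges. This is a cost answer with a gap in form completion. It is not something told to parents.
- *That F2's sentence on proceeding regardless of the study is false.* It comes before any study step and reads as the initial placement.
- *That parents were misled.* The consent form was not available, so only the protocol's wording can be judged.
- *That 11 to 27 children will have a study-caused repeat.* The arithmetic is 150 x 0.071 = 10.65 (the 7.1% bulging rate in G1) and 150 x 0.18 = 27 (the audit rate). Both treat an outside or clinical failure rate as a misplacement rate, and the audit rate is based on heart rate. Repeats directed by the collaborator are only the share that the provider misses, which is not given and could be anywhere from 0 to 100%.
- *That the MAC-hours comparison is biased by a known amount.* The above-1-MAC criterion describes only the failures, at incision, whereas MAC hours accumulate over the whole anesthetic. Objective 4 may also regard a lower target as part of what is being tested. What remains is that a difference cannot be attributed to confirmation alone.

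**Conclusion.** The point holds as an inconsistency in consent and risk wording. J2 and Section I are inaccurate against F2, and Section H omits a physical risk that the study can cause. The scan and the stated judgment reach all 150 children. The repeat placement reaches an unknown number, and no count is claimed. The harm from a repeat under general anesthesia is small. The primary outcome, the failure rate of blind placement, is unaffected.

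This rests on reading the blind technique as usual care, which the background text and Section I support, and on the protocol text alone. The consent document may already say the right thing.

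On objective 4, the supportable conclusion is a limit on interpretation, not a demonstrated bias: the comparator is non-concurrent and not shown to have used the 0.8-1 MAC window. The correction should be made, because J2 is a standing instruction to staff and putting it right is nearly free.

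**What to change.** - **J2 and Section I:** replace the no-change statements with text to this effect: *the initial block follows usual practice; the study adds an ultrasound scan by a collaborator, with the provider placing the block unable to see the image, a statement by that provider on whether placement is correct, and a possible repeat placement on the collaborator's instruction.* List the 0.5 mL saline injection and the 0.8-1 MAC window as well, unless they are usual local practice.
- **Section H:** add the small risk of a repeat needle placement, performed under general anesthesia.
- **Section L:** list the ultrasound as a research procedure at no charge.
- **Consent document:** check that it matches.
- **Leave unchanged:** the E2 assurance against coercion and the F2 sentence on the initial block.
- **G2 (secondary):** add a sentence that the MAC-hours comparator is a non-concurrent audit group not shown to have used the 0.8-1 MAC window, so a difference will not be attributed to ultrasound confirmation alone.

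The cost is a few sentences and one document check, with no change to sample size or procedures. The downside is a slightly less favorable risk statement and a more limited conclusion for objective 4.

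### Ultrasound is both the method under comparison and the only reference for placement, so the study cannot test Section I's hoped-for superiority: ultrasound can tie or win but cannot be shown worse or mistaken

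*Combined protocol and SAP*

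**What the plan says.** - **Section I (benefit to society)** names a possible finding: "should it show that ultrasound is superior for recognizing incorrect placement when compared with blind technique".
- **Section D, objective 1**, is to "Identify the rate at which blindly placed caudal blocks are not within the epidural space". G1 makes the blind failure rate the primary outcome and sizes the study for a gain in success rate, with each child as its own comparator.
- **F2** keeps the provider blinded to the image. After a 0.5 mL saline injection, "The provider will then be asked to state if they are correctly in the caudal space or not". A provider who thinks the placement is wrong repeats it. Otherwise, "If the provider fails to identify incorrect location and this is noted by ultrasound, the SC will inform the provider to re-do the procedure". The case moves on "After a successful injection (as confirmed by ultrasound) is performed".
- **Heart rate** is recorded later in F2: "The anesthesia provider will note the heart rate immediately before and after the first surgical stimulation". Objective 3 gives it this role: "Identify if lack of heart rate change on incision can predict successful placement when medication administration is successfully confirmed with ultrasound".
- **G2** plans odds ratios with 95% confidence intervals for the primary outcome. It plans no analysis of ultrasound accuracy and does not say which groups the odds ratio compares.

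**The concern.** To show that one method recognizes misplacement better than another, both must be measured against something that is neither of them. Here one of the two is the yardstick. When provider and ultrasound disagree over a placement that the provider accepted, ultrasound is taken as right.

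Two things are at stake. The first is the conclusion: a report could present as a finding something that the scoring rule guarantees whenever such a disagreement occurs. The second is the primary rate. It is a rate of ultrasound-read misplacement, and it equals the true rate only if ultrasound makes no errors or its errors happen to cancel. The planned confidence interval covers sampling error only.

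**Working it through.** **1. What the scoring allows.** Each first placement has a provider verdict and an ultrasound verdict.

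| Provider | Ultrasound | Under F2 |
|---|---|---|
| in | in | accepted; a misplacement that both overlook counts as correct |
| out | out | repeated; recognized by both |
| in | out | repeated; a provider miss, even if ultrasound is wrong |
| out | in | repeated on the provider's word; F2 does not say how it is scored |

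With ultrasound as the reference, its own count of unrecognized misplacements is zero by definition and the provider's is zero or more. A tie is possible; a result against ultrasound is not.

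**2. Whether other data could act as a check.** Heart rate is taken only after ultrasound confirmation. It might expose some false confirmations, but the plan does not use it for that. It cannot expose false alarms, because a block that ultrasound calls wrong is repeated and its clinical effect is never seen.

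**3. Effect on the primary rate.** Inputs from the documents: 7.1% failure (G1, an earlier study), 18% failure (background section, local review, defined by heart rate), and 150 children (G1). Ultrasound sensitivity (Se) and specificity (Sp) for misplacement are assumptions, since the documents give none. I take one placement per child.

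Apparent rate = p × Se + (1 − p) × (1 − Sp).

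With p = 0.071 and Se = 1:

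| Correct placements misread | Apparent rate | False alarms among 150 |
|---|---|---|
| 2% | 0.071 + 0.929 × 0.02 = 9.0% | 150 × 0.929 × 0.02 = 2.8 |
| 5% | 0.071 + 0.929 × 0.05 = 11.7% | 150 × 0.929 × 0.05 = 7.0 |
| 10% | 0.071 + 0.929 × 0.10 = 16.4% | 150 × 0.929 × 0.10 = 13.9 |

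Sampling half-width: 1.96 × √(0.071 × 0.929 / 150) = 4.1 points. The bias is 1.9, 4.6 and 9.3 points, so it is below the half-width at 2% and above it at 5% and 10%.

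With imperfect sensitivity as well:

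| Se / Sp | True rate 7.1% | True rate 18% |
|---|---|---|
| 95% / 98% | 0.0675 + 0.0186 = 8.6% | 0.171 + 0.0164 = 18.7% |
| 95% / 95% | 0.0675 + 0.0465 = 11.4% | 0.171 + 0.041 = 21.2% |
| 90% / 90% | 0.0639 + 0.0929 = 15.7% | 0.162 + 0.082 = 24.4% |

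The bias can also be downward: with Se = 90% and Sp = 100%, 7.1% becomes 0.071 × 0.90 = 6.4%.

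**4. Effect on provider misses.** Suppose that the true rate is 7.1%, that the provider recognizes half of true misplacements and accepts every correct placement, and that ultrasound has Se = Sp = 95%, with independent errors. Provider accuracy is 0.071 × 0.5 + 0.929 = 96.5%; ultrasound accuracy is 95%. Expected scored provider misses are 150 × (0.071 × 0.95 × 0.5 + 0.929 × 0.05) = 12.0. Of these, 7.0 (58%) are ultrasound false alarms. The method that is less accurate overall in this example is scored as making no error.

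G1's requirement of 99 children plays no part in these steps.

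**The case against.** The strongest reply is that Section I is a conditional benefit statement, not one of the four objectives, and that G2 plans no test of ultrasound against provider recognition. That is correct and limits the weight of the point. It does not remove it, because objectives 1 and 2 and the primary rate rest on the same reading.

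Four stronger readings are tempting and are not supported:

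- *That superiority is assured whatever the data.* If the two verdicts rarely or never disagree, superiority is not shown.
- *That every ultrasound misreading becomes a provider error.* Only a false alarm that the provider contradicts does. A misplacement that both accept counts as correct for both.
- *That all disagreements run one way, so a paired test would soon be significant.* A provider verdict of out against an ultrasound verdict of in is an opposite disagreement. F2 leaves its scoring open, and no paired test is planned.
- *That the primary rate is known to be inflated by several points.* The error rates are assumed, and Se = 1 gives the largest upward bias for a given specificity. At 95%/98% and a true rate of 18%, the shift is only 0.7 points.

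It can also be said that the data sheet attached to F2 is not in the available text. The absence of an independent reference is therefore established only for what can be read.

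**Conclusion.** The point holds in this form: on F2's scoring, ultrasound cannot be shown to be worse or mistaken, so the study can measure disagreement with ultrasound but cannot establish that ultrasound is better at recognizing misplacement. The same dependence reaches the success-rate gain in G1, since success is itself ultrasound confirmation.

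The structural part needs no assumption beyond the readable text. The size of the bias in the primary rate is unknown. The illustrative range of 9.0% to 16.4% for a true 7.1% rests on assumed specificities of 98% to 90% and perfect sensitivity. The change should be made: it alters what the trial may conclude, though not how it is run.

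**What to change.** 1. **Section I.** Replace the superiority wording with, for example: *The study will describe how often the blinded provider's verdict on placement disagrees with the ultrasound reading, in each direction.*
2. **G2.** Label the primary rate *ultrasound-read misplacement*. Report it as x/n with an exact 95% confidence interval, rather than as an odds ratio of ultrasound against blind placement. Report in the same way the proportion of ultrasound-read misplacements that the provider did not recognize. At 7.1%, its denominator is only about 150 × 0.071 = 11 children if ultrasound reads without error, so that interval will be wide. State that no conclusion of superior recognition will be drawn, because ultrasound is the reference.
3. **Optional.** State the possible effect of ultrasound misreading as a limitation. Any sensitivity table should vary both sensitivity and specificity and truncate at 0. Correcting an observed 7.1% for 10% false alarms alone gives (0.071 − 0.10) / 0.90 = −3.2%, which is impossible, and it ignores missed misplacements.

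The cost is a few sentences in Section I and G2, with no extra children or procedures. The sponsor gives up a superiority conclusion that this design cannot support.
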